2.15	Distance logMAR VA with spherocylindrical prescription	
Measure distance ETDRS logMAR visual acuity at a 4 meter (m) distance with the spherocylindrical prescription measured at V1 in a trial frame using the conditions and charts shown in the table below:
 
 
 Distance	4 m	4 m	
 
 Condition	HLHC	HLHC	
 
 Room illumination	686-788 lux	686-788 lux	
 
 Chart luminance	181-208 cd/m²	181-208 cd/m²	
 
 Eye	OD	OS	
 
 Charts (Numbers)	HC-3 (2114B)	HC-4 (2114C)	
 
 
Note: If logMAR VA measures more than 0.15 logMAR worse than at baseline, the measurement should be repeated. If the visual acuity reduction is confirmed, an adverse event will be filed. The subject will be followed until visual acuity is no more than 0.15 logMAR worse than baseline or is stabilized before being discontinued.
	Distance	4 m	4 m	Condition	HLHC	HLHC	Room illumination	686-788 lux	686-788 lux	Chart luminance	181-208 cd/m ²	181-208 cd/m ²	Eye	OD	OS	Charts (Numbers)	HC-3 (2114B)	HC-4 (2114C)
Distance	4 m	4 m																		
Condition	HLHC	HLHC																		
Room illumination	686-788 lux	686-788 lux																		
Chart luminance	181-208 cd/m ²	181-208 cd/m ²																		
Eye	OD	OS																		
Charts (Numbers)	HC-3 (2114B)	HC-4 (2114C)																		

Clinical Study Protocol
Johnson & Johnson Vision Care, Inc.

Visit 2: CL Fit		
Step	Procedure	Details
		
Note 2: per ISO 11980, a loss of two or more lines (0.20 logMAR) of best corrected visual acuity for greater than or equal to 2 weeks is considered a significant or serious adverse event depending on the duration.

2.16	Lens Selection	
Assign the study lenses based on the randomization schedule.
 
Select the appropriate power of the contact lenses based on subjective best sphere refraction (completed at V1) and adjust for vertex distance to the corneal plane if needed (< -4.00 D). Record the lens parameters.

2.17	Lens Insertion	
The subject applies the study lenses. If a lens is uncomfortable, inspect for damage and remove, reinsert or replace as necessary.
 
Check for lens damage under the slit lamp before proceeding with lens settling. Replace damaged lenses if applicable. Record the time of lens insertion.

2.18	Right eye number insertion attempts	
Record the number of attempts that were necessary to successfully insert the lens into the right eye.
 
If more than 1 insertion attempt was necessary, or the patient otherwise experienced significant difficulty inserting the lens, record the primary reason for difficulty with the lens insertion:
 
 • Lens did not leave finger • Lens folded on finger • Lens inverted on finger • Lens touched eyelid/eyelashes as it moved towards eye • Lens did not settle on eye or was blinked out • Other (specify reason)

Clinical Study Protocol
Johnson & Johnson Vision Care, Inc.

Visit 2: CL Fit		
Step	Procedure	Details
2.19	Left eye number insertion attempts	
Record the number of attempts that were necessary to successfully insert the lens into the right eye.
 
If more than 1 insertion attempt was necessary, or the patient otherwise experienced significant difficulty inserting the lens, record the primary reason for difficulty with the lens insertion:
 
 • Lens did not leave finger • Lens folded on finger • Lens inverted on finger • Lens touched eyelid/eyelashes as it moved towards eye • Lens did not settle on eye or was blinked out • Other (specify reason)
2.20	Lens Settling	Allow the study lenses to settle for a minimum of 10 minutes.
2.21	Lens-on-eye Distance VA	Record the distance Snellen visual acuity (OD, OS) to the nearest letter with the study lenses in place. Subjects must read the smallest line until at least 50% of the letters are read incorrectly.
2.22	Monocular Subjective Best Sphere Over Refraction	
Perform monocular subjective best sphere refraction over the study lenses with a phoropter.
 
 • Reduce minus (add plus) in 0.25 D steps if there is no decrease in visual acuity and no subjective vision reduction. • Increase minus in 0.25 D steps if it significantly improves distance vision. • Record the spherical power and the resultant distance visual acuity to the nearest letter (OD, OS).

Clinical Study Protocol
Johnson & Johnson Vision Care, Inc.

Visit 2: CL Fit		
Step	Procedure	Details
2.23	General Lens Fit Assessment	
Evaluate lens centration, movement on blink, and push-up test for each eye.
 
An unacceptable fit is deemed by one of the following criteria:
 
 • limbal exposure at primary gaze or with extreme eye movement. • edge lift. • excessive movement in primary and up gaze. • insufficient movement in all three of the following conditions: primary gaze, up gaze, and push-up test. 
Note: if lens fit is unacceptable for either eye, the subject will be discontinued from the study.

2.24	Lens Power Modification (if applicable)	
Refer to the respective fitting guide to determine whether a lens power modification is needed.
 
For each power modification, select the new lens power as appropriate and repeat the steps beginning with right lens insertion.
 
A maximum of 2 lens modifications are allowed per eye. If, for either eye, the fit is not successful after 2 modifications, the subject will be discontinued proceed to final evaluation.

2.25	Subject Reported Ocular Symptoms	Subjects will respond to a verbal open-ended symptoms questionnaire.
2.26	Post-Fit Questionnaire	Subjects will complete a PRO questionnaire regarding the initial comfort and handling of the study lenses.
2.27	Contact Lens Checklist	Ask the subject to complete the Contact Lens Checklist (repeat until the subject can answer all the questions correctly) and continue with lens dispensing.

Clinical Study Protocol
Johnson & Johnson Vision Care, Inc.

Visit 2: CL Fit		
Step	Procedure	Details
2.28	Continuance (Lens Dispensing Criteria)	
For the subject to continue in the study, they must meet all five of the following criteria:
 
 1. The subject's distance visual acuity with the test article must be equal to or better than 20/25 in each eye. 2. The subject indicates that the comfort and vision with the study lenses is acceptable. 3. The lens fit is acceptable in both eyes. 4. Investigator approval. If the Investigator does not approve the dispensing of the study lens, then the study is terminated for that subject. 5. The subject has successfully answered all questions in the Contact Lens Checklist correctly.
2.29	Lens Dispense	
The lenses will be dispensed for a wearing period of 11 to 17 days. The lenses will be worn as daily wear/daily disposable only.
 
At the investigator's discretion, provide the subject with rewetting drops approved in local markets. No disinfecting or storage solutions will be given to the subject.
 
Study contact lens dispensing instruction checklist:
 
 1. Habitual contact lens wearers should wear the study lenses at least 8 hours a day, 5 days a week (recommend 10 hours or more a day, 7 days a week) until the next visit. 2. Never sleep in the lenses. 3. Always throw away any lens that is taken out of the eye and use only the new lens with each lens insertion. 4. Always have eyeglasses at hand while wearing the study contact lenses. 5. When not wearing the study contact lenses, only the habitual spectacles (no contact lenses) should be worn.

Clinical Study Protocol
Johnson & Johnson Vision Care, Inc.

Visit 2: CL Fit		
Step	Procedure	Details
		
6. Schedule the subject for the next visit (11 to 17 days from Visit 2). 7. Instruct the subject to wear study lenses to the next visit.
 
Note: In the event a lens is lost or damaged, the subject will use a new lens from the most recently dispensed lenses. As much as reasonably possible, a damaged lens and packaging should be returned to the clinical site (wet, if possible) and then returned to the Sponsor. If lens damage is present, site staff will complete the Product Quality Complaint Form. The lens will be stored in labeled vial with saline, and clearly differentiated from the other worn lenses that may be returned to the Sponsor, if any.

2.30	Schedule next visit	
Schedule the follow-up visit to occur in 14 ± 3 days (counting the day of this visit as day 0, the subject may return on day 11 through 17). Ensure the subject is instructed to wear the study lenses for at least 1 hour(s) immediately prior to attending the follow-up visit.

VISIT 3

The subjects must present to Visit 3 wearing the study lenses and having worn them continuously for at least 1 hour on the day of the visit immediately prior to attending the visit.

Visit 3: CL Follow-Up

The steps followed will be the same as those listed under Visit 2: CL Follow-Up. The only difference is that the randomization step will not be repeated.

Visit 3: CL Fit

The steps followed will be the same as those listed under Visit 2: CL Fit.

Clinical Study Protocol

Johnson & Johnson Vision Care, Inc.

VISIT 4

The subjects must present to Visit 4 wearing the study lenses and having worn them continuously for at least 1 hour on the day of the visit immediately prior to attending the visit.

Visit 4: CL Follow-Up

The steps followed will be the same as those listed under Visit 2: CL Follow-Up. The only difference is that the randomization step will not be repeated.

Visit 4: CL Fit

The steps followed will be the same as those listed under Visit 2: CL Fit.

VISIT 5

The subjects must present to Visit 5 wearing the study lenses and having worn them continuously for at least 1 hour on the day of the visit immediately prior to attending the visit.

Visit 5: Follow-Up		
Step	Procedure	Details
5.1	Change of Medical History (Adverse Events) and Concomitant Medications / Therapies Review	Record any adverse events or medical history changes from the previous study visit with the subject/parents. Review the subject's concomitant medications/therapies and record any changes from the previous study visit.
5.2	Contact Lens Wearing Time and Compliance	Record the average wearing time and confirm compliance with the prescribed wear schedule. The subjects will be asked the time of the day they typically apply the study lenses in the morning and take off in the evening, the number of days per week lenses were worn, and the number of consecutive days the subject didn't wear the study lenses (if applicable), etc.
5.3	Compliance	Confirm compliance with the prescribed wear schedule.
5.4	Unworn lens return	Subject to return any unworn investigational lenses.

Clinical Study Protocol
Johnson & Johnson Vision Care, Inc.

Visit 5: Follow-Up																														
Step	Procedure	Details																												
5.5	PRO Follow-up and PROMIS PGH7 Questionnaires	
The subject will complete a PRO questionnaire to assess their experience with the study lenses and a general health questionnaire.
																												
5.6	Subject Reported Ocular Symptoms	
Subjects will respond to a verbal open-ended symptoms questionnaire.
																												
5.7	Distance Visual Performance	
Measure distance ETDRS logMAR visual acuity at a 4 meter (m) distance with the subject wearing the study lenses using the conditions and charts shown in the table below:
 
For low luminance measures, the mesopic filter should be used to reduce luminance to the range specified below. Allow subjects to adapt to dim illumination for at least 3 minutes before testing the LLHC condition.
 
  
 Distance	4 m	
 
 Condition	HLHC	HLLC	LLHC	
   
 Room illumination	686-788 lux	686-788 lux	1.4-1.6 lux	
 
 Chart luminance	181-208 cd/m²	
 
 Eye	OU	OD	OU	
 
 Charts (Numbers)	HC-1 (2214)	HC-2 (2214A)	LC-1 (2164)	
 
 	LC-2 (2164A)	HC-3 (2114B)	HC-4 (2114C)	
  
	Distance	4 m			Condition	HLHC	HLLC	LLHC	Room illumination	686-788 lux	686-788 lux	1.4-1.6 lux	Chart luminance	181-208 cd/m ²			Eye	OU	OD	OU	Charts (Numbers)	HC-1 (2214)	HC-2 (2214A)	LC-1 (2164)		LC-2 (2164A)	HC-3 (2114B)	HC-4 (2114C)
Distance	4 m																													
Condition	HLHC	HLLC	LLHC																											
Room illumination	686-788 lux	686-788 lux	1.4-1.6 lux																											
Chart luminance	181-208 cd/m ²																													
Eye	OU	OD	OU																											
Charts (Numbers)	HC-1 (2214)	HC-2 (2214A)	LC-1 (2164)																											
	LC-2 (2164A)	HC-3 (2114B)	HC-4 (2114C)																											
5.8	Near Visual Performance	
Measure near ETDRS logMAR visual acuity at a 40 centimeter distance with the subject wearing the study lenses using the conditions shown in the table below:
 
  
 Distance	40 cm	40 cm	
 
 Condition	HLHC	HLLC	
   
 Room illumination	686-788 lux	686-788 lux	
 
 Chart luminance	225 - 275 cd/m²	225 - 275 cd/m²	
 
 Eye	OU	
  
	Distance	40 cm	40 cm	Condition	HLHC	HLLC	Room illumination	686-788 lux	686-788 lux	Chart luminance	225 - 275 cd/m ²	225 - 275 cd/m ²	Eye	OU														
Distance	40 cm	40 cm																												
Condition	HLHC	HLLC																												
Room illumination	686-788 lux	686-788 lux																												
Chart luminance	225 - 275 cd/m ²	225 - 275 cd/m ²																												
Eye	OU																													

Clinical Study Protocol
Johnson & Johnson Vision Care, Inc.

Visit 5: Follow-Up				
Step	Procedure	Details		
		Charts (Numbers)	HC-1 (2106C)	LC-1 (2118)
5.9	Monocular Subjective Best Sphere Over Refraction	
Perform monocular subjective best sphere refraction over the study lenses with a phoropter.
 
 • Reduce minus (add plus) in 0.25 D steps if there is no decrease in visual acuity and no subjective vision reduction. • Increase minus in 0.25 D steps if it significantly improves distance vision. • Record the spherical power and the resultant distance visual acuity to the nearest letter (OD, OS). 		
5.10	General Lens Fit Assessment	
Evaluate lens centration, movement on blink, and push-up test for each eye.
 
An unacceptable fit is deemed by one of the following criteria:
 
 • limbal exposure at primary gaze or with extreme eye movement. • edge lift. • excessive movement in primary and up gaze. • insufficient movement in all three of the following conditions: primary gaze, up gaze, and push-up test. 
Note: if lens fit is unacceptable for either eye, the subject will be discontinued from the study.
		
5.11	Wettability Characteristics	Record the white light lens wettability of both lenses.		
5.12	Surface Deposits	Record any front and back surface lens deposits.		
5.13	Lens Removal	
Remove the study contact lenses. If either removed lens is associated with a PQC or adverse event, add solution to the lens vial for storage prior to return shipment to JJVC.
 
If no adverse event or PQC is associated with the lenses they can be properly disposed.
		

Clinical Study Protocol
Johnson & Johnson Vision Care, Inc.

Visit 5: Follow-Up																				
Step	Procedure	Details																		
5.14	Slit Lamp Biomicroscopy	
Slit Lamp Classification Scale per ISO 11980 will be used to grade the findings. If the clearance of the fluorescein needs to be expedited, preservative-free rewetting drops or saline may be instilled.
 
Note: If any slit lamp finding is graded as 2 (except for subjects with Grade 2 baseline palpebral conjunctival observations) or worse, it may warrant classification of an adverse event, and shall be followed accordingly. A subject with significant slit lamp findings (e.g., Grade 3 corneal staining, Grade 2 corneal neovascularization, anterior segment inflammation, and corneal infiltrate, etc.) an adverse event form must be completed. The subject must be followed until slit lamp findings are resolved.
																		
5.15	Distance logMAR VA with spherocylindrical prescription	
Measure distance ETDRS logMAR visual acuity at a 4 meter (m) distance with spherocylindrical prescription in a trial frame using the conditions and charts shown in the table below:
 
 
 Distance	4 m	4 m	
 
 Condition	HLHC	HLHC	
 
 Room illumination	686-788 lux	686-788 lux	
 
 Chart luminance	181-208 cd/m²	181-208 cd/m²	
 
 Eye	OD	OS	
 
 Charts (Numbers)	HC-3 (2114B)	HC-4 (2114C)	
 
 
Note: If logMAR VA measures more than 0.15 logMAR worse than at baseline, the measurement should be repeated. If the visual acuity reduction is confirmed, an adverse event will be filed. The subject will be followed until visual acuity is no more than 0.15 logMAR worse than baseline or is stabilized before being discontinued.
	Distance	4 m	4 m	Condition	HLHC	HLHC	Room illumination	686-788 lux	686-788 lux	Chart luminance	181-208 cd/m ²	181-208 cd/m ²	Eye	OD	OS	Charts (Numbers)	HC-3 (2114B)	HC-4 (2114C)
Distance	4 m	4 m																		
Condition	HLHC	HLHC																		
Room illumination	686-788 lux	686-788 lux																		
Chart luminance	181-208 cd/m ²	181-208 cd/m ²																		
Eye	OD	OS																		
Charts (Numbers)	HC-3 (2114B)	HC-4 (2114C)																		

Clinical Study Protocol
Johnson & Johnson Vision Care, Inc.

Visit 5: Follow-Up		
Step	Procedure	Details
		
Note 2: per ISO 11980, a loss of two or more lines (0.20 logMAR) of best corrected visual acuity for greater than or equal to 2 weeks is considered a significant or serious adverse event depending on the duration.

FINAL EVALUATION

The final evaluation will ordinarily take place immediately following the last scheduled follow-up visit per the study protocol. It may also take place at any point the subject discontinues the study or is terminated from the study.

Final Evaluation		
Step	Procedure	Details
F.1	Final Exam Form	Indicate if the subject completed the study successfully. If subject discontinued from the study, indicate the reason.
F.2	Exit Refraction	
Perform bare-eye subjective spherocylindrical refraction with a phoropter and record the best-corrected distance visual acuity (OD and OS) to the nearest letter.
 
Note: This step is not necessary if the subject was exited due to screen failure.

F.3	Exit Slit Lamp Biomicroscopy (for subjects that are discontinued early)	
Slit Lamp Classification Scale per ISO 11980 will be used to grade the findings. If the clearance of the fluorescein needs to be expedited, preservative-free rewetting drops or saline may be instilled.
 
Note: If any slit lamp finding is graded as 2 (except for subjects with Grade 2 baseline palpebral conjunctival observations) or worse, it may warrant classification of an adverse event, and shall be followed accordingly. A subject with significant slit lamp findings (e.g., Grade 3 corneal staining, Grade 2 corneal neovascularization, anterior segment inflammation, and corneal infiltrate, etc.) requires an adverse event form to be

Clinical Study Protocol
Johnson & Johnson Vision Care, Inc.

Final Evaluation		
Step	Procedure	Details
		completed. The subject must be followed until slit lamp findings are resolved.

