2.2. Endpoints

Primary efficacy endpoint:

- Binocular distance (4 m) high luminance high contrast (HLHC) logMAR visual acuity, measured per [REDACTED]

Primary safety endpoint:

- Number (n, %) of subjects and eyes with contact lens related (i.e., related and possibly related) serious and significant ocular adverse events (AEs), including best corrected logMAR loss ≥ 0.20 logMAR (10 letters).

Other exploratory endpoints:

- Monocular HLHC logMAR visual acuity at 4 m
- Binocular high luminance low contrast (HLLC) logMAR visual acuity at 4 m
- Monocular HLLC logMAR visual acuity at 4 m
- Binocular low luminance high contrast (LLHC) logMAR visual acuity at 4 m
- Monocular LLHC logMAR visual acuity at 4 m
- Binocular HLHC logMAR visual acuity at 40 cm
- Binocular HLLC logMAR visual acuity at 40 cm
- Subjective vision, comfort, and ease of handling
- Non-significant AEs and non-ocular AEs
- Slit lamp findings per the ISO 11980 grading scale
- Subject-reported ocular symptoms
- Number of contact lens insertion attempts per eye at fitting
- Subjective best sphere over-refraction with the first trial lens
- Subjective best sphere over-refraction at follow-up
- Number of power modifications at fitting
- Lens fitting characteristics

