7.2. Detailed Study Procedures

VISIT 1

Subjects should bring spectacles with them to Visit 1, if applicable. The subjects must present to Visit 1 wearing spectacles or uncorrected, not having worn contact lenses on the day of the visit.

Visit 1: Screening		
Step	Procedure	Details
1.1	Statement of Informed Consent & Children's Assent	
Each subject's parent or legal guardian must read, understand, and sign the Statement of Informed Consent (Parental Permission Form and Authorization to Use and Disclose Medical Information), and each subject must read (or be read to), understand and sign the Information and Assent Form before the subject is enrolled into the study.
 
The Principal Investigator or his/her designee conducting the informed consent discussion must also sign the Consent and Assent forms.
 
Note: The subject and parent (legal guardian) must be provided a signed copy of both documents.

1.2	Demographics	Record the subject's year of birth, age, gender, race and ethnicity.
1.3	Medical History and Concomitant Medications	Record the subject's medical history and concomitant medications.
1.4	Habitual Contact Lenses (if applicable)	Record the subject's habitual lens type, parameters, lens care solution (if applicable), wear modality and approximate prescription date.
1.5	Habitual Lens Wear Time (if applicable)	Record the subject's duration of lens wear in years and months, minimum days worn per week, and average daily wear time for their habitual lenses.

Clinical Study Protocol
Johnson & Johnson Vision Care, Inc.

Visit 1: Screening		
Step	Procedure	Details
1.6	Eligibility after Screening	
All responses to Screening Inclusion Criteria questions must be answered “yes” and all responses to Exclusion Criteria must be answered “no” for the subject to be considered eligible.
 
Note: If subject is deemed to be ineligible after screening, proceed to Final Evaluation and complete Subject Disposition. Refraction and Biomicroscopy forms are not required.

Visit 1: Baseline		
Step	Procedure	Details
1.7	PRO Questionnaire (PROMIS PGH7 only)	Subjects will complete a PRO questionnaire.

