1.8	Entrance Visual Acuity	
Record the monocular distance Snellen visual acuity for each eye (OD, OS) to the nearest letter with the subject’s habitual eyeglasses or uncorrected. Subjects must continue until at least 50% of the letters on a line are read incorrectly.
 
Note: Subject must have 20/40 or better vision in each eye with habitual spectacles or uncorrected.

1.9	Keratometry/SimK	Record the keratometry or SimK readings OD and OS in diopters.
1.10	Subjective Spherocylindrical Refraction	Complete subjective spherocylindrical refraction and record the resultant distance visual acuity (OD, OS) to the nearest letter.
1.11	Subjective Best Sphere Refraction	Perform subjective best sphere refraction with a phoropter (adopt the maximum plus to maximum visual acuity (MPMVA) approach and record the best corrected distance visual acuity (OD, OS) to the nearest letter.

Clinical Study Protocol
Johnson & Johnson Vision Care, Inc.

Visit 1: Baseline																					
Step	Procedure	Details																			
1.12	Distance logMAR VA with spherocylindrical prescription	
Measure distance ETDRS logMAR visual acuity at a 4 meter (m) distance with spherocylindrical prescription in a trial frame using the conditions and charts shown in the table below:
 
 
 Distance	4 m	4 m	
 
 Condition	HLHC	HLHC	
 
 Room illumination	686-788 lux	686-788 lux	
 
 Chart luminance	181-208 cd/m²	181-208 cd/m²	
 
 Eye	OD	OS	
 
 Charts (Numbers)	HC-3 (2114B)	HC-4 (2114C)	
 
	Distance	4 m	4 m	Condition	HLHC	HLHC	Room illumination	686-788 lux	686-788 lux	Chart luminance	181-208 cd/m ²	181-208 cd/m ²	Eye	OD	OS	Charts (Numbers)	HC-3 (2114B)	HC-4 (2114C)	
Distance	4 m	4 m																			
Condition	HLHC	HLHC																			
Room illumination	686-788 lux	686-788 lux																			
Chart luminance	181-208 cd/m ²	181-208 cd/m ²																			
Eye	OD	OS																			
Charts (Numbers)	HC-3 (2114B)	HC-4 (2114C)																			
1.13	Cover Test	Perform distance and near cover-uncover test to rule out the presence of strabismus. Subject must be wearing distance vision correction during cover test assessment.																			

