2.12	Lens Removal	
Remove the study contact lenses. If either removed lens is associated with a PQC or adverse event, add solution to the lens vial for storage prior to return shipment to JJVC.
 
If no adverse event or PQC is associated with the lenses they can be properly disposed.

2.13	Slit Lamp Biomicroscopy	
Slit Lamp Classification Scale per ISO 11980 will be used to grade the findings. If the clearance of the fluorescein needs to be expedited, preservative-free rewetting drops or saline may be instilled.
 
Note: If any slit lamp finding is graded as 2 (except for subjects with Grade 2 baseline palpebral conjunctival observations) or worse, it may warrant classification of an adverse event, and shall be followed accordingly. A subject with significant slit lamp findings (e.g., Grade 3 corneal staining, Grade 2 corneal vascularization, anterior segment inflammation, and corneal infiltrate, etc.) may not be dispensed with the study contact lens at this time, and an adverse event form must be filled.

Clinical Study Protocol
Johnson & Johnson Vision Care, Inc.

Visit 2: CL Follow-Up		
Step	Procedure	Details
		
The subject must be followed until slit lamp findings are resolved and the investigator deems it's appropriate for the subject to continue with the study before study lens dispensing. If the subject is discontinued from the study, Final Evaluation must be completed.
 
If the clearance of the fluorescein needs to be expedited, preservative-free rewetting drops or saline may be instilled.

2.14	Washout	Wait 10 minutes from lens removal before proceeding with the next lens fit.

Visit 2: CL Fit																				
Step	Procedure	Details																		

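### The primary safety endpoint counts best-corrected acuity loss, but neither the follow-up reading nor its confirming repeat requires a current refraction

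*Combined protocol and SAP*

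**What the plan says.** Section 2.2 defines the primary safety endpoint as contact-lens-related serious and significant ocular adverse events, "including best corrected logMAR loss ≥ 0.20 logMAR (10 letters". It does not say which prescription the reading uses.

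Section 7.2 sets out the readings:

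- **Visit 1.** Step 1.12 follows a subjective spherocylindrical refraction on the same day (1.10).
- **Visits 2-4.** Step 2.15 is read "with the spherocylindrical prescription measured at V1 in a trial frame". Visits 3 and 4 refer back to the Visit 2 steps.
- **Visit 5.** Step 5.15 reads only "Measure distance ETDRS logMAR visual acuity at a 4 meter (m) distance with spherocylindrical prescription in a trial frame", without saying when that prescription was measured. The exit refraction comes afterwards, at F.2: "Perform bare-eye subjective spherocylindrical refraction with a phoropter and record the best-corrected distance visual acuity".
- **Repeat rule (2.15, 5.15 and U.8).** "If logMAR VA measures more than 0.15 logMAR worse than at baseline, the measurement should be repeated". A confirmed reduction is filed as an adverse event. The note requires no new refraction.
- **Unscheduled visits.** Refraction (U.7) is listed before logMAR acuity (U.8), but only if applicable.

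Section 13.5.2 has its own filing rule for the final visit. Acuity must be more than 1.5 lines worse than baseline and also below 20/25, confirmed by up to three independent measures.

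**The concern.** A reading is best-corrected only if it is taken with the current best correction. An older prescription can at best equal that correction. If refraction has moved since Visit 1, the reading mixes two things: a change in the eye's attainable acuity, which the endpoint is meant to detect, and a change in refraction, which it is not.

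The repeat reduces chance error. It does not separate these two components if the same prescription stays in the trial frame, because the part due to refraction is present in both readings. A child whose myopia has progressed slightly could therefore be confirmed as having lost acuity, have an adverse event filed and be followed up, although a new refraction would have restored the reading. Some of these events could go on to enter the primary safety tabulation.

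**Working it through.** **The plan's own figures.** The protocol gives no expected rate for this endpoint. Its only calculated design figures are the powers in Table 8 (section 14.2), for the efficacy comparison. All twelve reproduce with a paired t-test, SD of the difference = 0.084 × √(2(1 − ρ)) and one-sided 0.025. For example, 50 completers with difference 0 and ρ = 0.3 give 93.66% against the stated 93.7%. This point does not affect them.

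**Age of the prescription at Visit 5.** From the visit windows in Table 3:

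- nominal: 7 + 3 × 14 = 49 days
- range: 5 + 3 × 11 = 38 to 9 + 3 × 17 = 60 days
- with up to 14 further days for insertion and removal training (step 1.27): 74 days

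**Likely drift.** The MiSight package insert (Appendix C) gives mean first-year changes of −0.18 D with MiSight and −0.58 D with the single-vision control. Drift = annual rate × days / 365.25:

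| Annual rate | 49 days | 74 days |
|---|---|---|
| 0.18 D | 0.02 D | 0.04 D |
| 0.58 D | 0.08 D | 0.12 D |
| 0.77 D (control, 9-year-olds) | 0.10 D | 0.16 D |

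All are below one 0.25 D step. They are means for children aged 8-12, and individuals will vary. The documents give no conversion from dioptres to logMAR, so the shifts below are assumptions and are not derived from this table.

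**False confirmations in stable eyes.** Inputs:

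- SD of a follow-up-minus-baseline difference: section 13.5.2 bases the 1.5-line criterion on 95% limits of agreement, so SD = 0.15 / 1.96 = 0.0765.
- Correlation between the first and the repeat difference: 0.5. Both subtract the same baseline reading; with equal error variance σ², the covariance is σ² and each variance is 2σ².
- Eye-visits: 50 completers × 2 eyes × 4 visits (Visits 2-5) = 400.

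For a constant shift s and threshold c, the single-reading probability is 1 − Φ((c − s) / 0.0765). The confirmed probability is the chance that both of two standard normal variables with correlation 0.5 exceed (c − s) / 0.0765.

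| Shift s (assumed) | Single > 0.15 | Confirmed > 0.15 | Per 400 | Single ≥ 0.20 | Confirmed ≥ 0.20 | Per 400 |
|---|---|---|---|---|---|---|
| 0 | 2.5% | 0.46% | 1.8 | 0.45% | 0.04% | 0.2 |
| 0.02 | 4.5% | 1.04% | 4.2 | 0.93% | 0.12% | 0.5 |
| 0.04 | 7.5% | 2.17% | 8.7 | 1.83% | 0.30% | 1.2 |

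If 0.15 is instead read as a one-sided 95% bound, SD = 0.15 / 1.645 = 0.0912. The confirmed counts per 400 become 4.9, 9.0 and 15.6 over 0.15, and 0.8, 1.8 and 3.5 at 0.20 or more.

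These counts are taken before the 2-week and relatedness filters.

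**The case against.** **Filters stand between a low reading and the endpoint.** Note 2 of step 2.15 and section 13.1 make a temporary two-line loss significant only if it lasts at least two weeks. The endpoint also requires the event to be related or possibly related. This stands: a confirmed loss over 0.15 leads to an adverse event filing, not automatically to a primary safety event. The 2-week rule is an incomplete screen, because the next scheduled visit (14 ± 3 days) uses the same prescription.

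**Drift is small and a fixed correction is defensible.** At Visit 2 the prescription is normally about a week old, and holding it constant makes successive readings comparable. This also stands and limits the size of the point. It does not make the reading best-corrected.

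**Partial safeguards exist.** F.2 gives a freshly refracted acuity at exit, and U.7 can precede U.8. Neither is required before a loss is confirmed, and F.2 does not specify the logMAR chart conditions.

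**No decision turns on it.** Section 14.5 tabulates safety without a test or threshold, and a shift largely common to all lenses in a balanced crossover cancels from the comparison. This is correct.

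**A stronger reading is tempting.** A reader might infer that lens wear and dye before the follow-up reading, with no wait at Visit 5, bias it toward loss. The baseline visit does require "not having worn contact lenses on the day of the visit" and does place acuity before the slit lamp. But the documents do not say that an hour of wear or fluorescein lowers trial-frame acuity, and they allow drops or saline to clear the dye. Such effects would also be transient, so a later repeat could reduce them. Step 2.14 reads "Wait 10 minutes from lens removal before proceeding with the next lens fit": it is timed from lens removal, so it is not a wait after dye, and Visit 5 has no next fit. Charts HC-3 and HC-4 are reused at every visit, so practice could push follow-up readings the other way. The net direction is unknown.

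**Conclusion.** The point holds as a mismatch between the endpoint's definition and its measurement. The Visit 1 prescription is explicit for Visits 2-4. For Visit 5 it is inferred, because no other scheduled refraction comes before step 5.15. At no visit must a loss be confirmed with a current refraction.

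The expected effect is small: mean drift of about 0.02-0.08 D by the nominal Visit 5, and 0.12 D over 74 days at the insert's overall single-vision rate. Under the assumed shifts, the main consequence is a few avoidable adverse event filings; confirmed losses of 0.20 or more stay near one per 400 eye-visits or fewer. This rests on normal errors, SD 0.0765, correlation 0.5 and shifts that no document figure supports.

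Two further inferences do not follow. Single-reading rates are not event rates, because the protocol requires a repeat: at a shift of 0.04 the rate for 0.20 or more falls from 1.83% to 0.30%. And the lens comparison is not materially biased; what is affected is the absolute event count. This is an inexpensive improvement, not a flaw that threatens the trial's conclusions.

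**What to change.** 1. At Visit 5, perform the already planned F.2 refraction before step 5.15, and state that 5.15 uses that prescription.
2. At Visits 2-4 and unscheduled visits, when a reading is more than 0.15 logMAR worse than baseline, make the confirming repeat after a fresh subjective refraction by the U.7 method, and classify the loss on that reading.
3. Reconcile the filing rule in step 5.15 (more than 0.15 worse) with section 13.5.2, which also requires acuity below 20/25. The two passages give different rules for the same visit.

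The cost is one reordered step and a few minutes' refraction for the few flagged eyes, with no extra visits. The downside is that the Visit 5 prescription may differ from the one used at Visits 2-4, so the report should state which prescription each reading used.
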